# **1.0 STUDY SUMMARY**

# **1.1 AIM AND HYPOTHESIS**

The objective of this project is to compare the efficacy of hyoscyamine to tamsulosin monotherapy in treating lower urinary tract symptoms in patients with indwelling double-J ureteral stents.

Ureteral stents are routinely used in a variety of urologic conditions. Unfortunately, indwelling ureteral stents commonly cause significant pain and discomfort due to irritation to the urinary system. Many studies have looked at methods to reduce these uncomfortable symptoms ranging from altering stent designs to pharmacologic therapies attempting to alleviate stent-discomfort. However, stent-related discomfort continues to be an issue and is often the cause of their removal earlier than planned. While the efficacy of certain alpha blockers and anticholinergics in treating stent-related symptoms have been studied, the data for the use of hyoscyamine in this setting is lacking. A literature search yielded no studies evaluating the use of hyoscyamine in this setting to date. We hypothesize that hyoscyamine (brand name Levsin) is equivalent to tamsulosin in treating lower urinary tract symptoms in patients with indwelling double-J ureteral stents due to its anticholinergic properties. Furthermore, we hypothesize that patients in the hyoscyamine arm will not require additional pain medications (e.g. Pyridium, narcotics) to help control stent-related discomfort compared to the tamsulosin arm.

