# **3.2 SECONDARY OBJECTIVE**

To determine if there is a difference between the amount of additional medications needed to treat stent related discomfort between patients receiving hyoscyamine versus those that receive tamsulosin.

To determine factors contributing to patients needing additional medication for treatment of stent-related discomfort.

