The first arm is hyoscyamine 0.125 mg tab sublingual every 4 hours as needed for discomfort, and the second arm is tamsulosin 0.4mg tab orally daily. Both dosing regimens are standard prescription orders. Both medications are routinely used in our practice, so patients are not being exposed to new safety risks compared to non-study patients. Risks are reasonable, as the medications used in this study are already commonly used in our daily practice. Patients will be given contact numbers for the Urology Department should they have any adverse side effects or concerns. Hyoscyamine is an anticholinergic and can cause side effects including constipation, dry mouth, drowsiness, headache, or lightheadedness. Tamsulosin is an alpha blocker and can

cause side effects including dizziness, fatigue, nasal congestion, syncope and retrograde ejaculation. Patients who have taken alpha blockers are at risk for intraoperative floppy iris syndrome if they are going a cataracts surgery in the near future. Patients will be advised to immediately stop the medicine and seek medical care if they develop the rare but severe reactions of skin rash, swelling, confusion, irregular or fast heartbeat, eye pain, or hallucinations. As part of the standard treatment pathway for post-stent insertion, patients are also sent home with a narcotic pain medication to help with pain and discomfort. Our pathway is to prescribe all patients with 10 tabs of Norco 5/325 1-2 tabs po q6H PRN unless there are contraindications or allergies to this specific narcotic, in which case they are prescribed an alternative narcotic with Percocet 5/325 1-2 tabs po q6H PRN. Patients will be given a drug diary to document their usage of the study medications for stent discomfort, including their narcotic usage, so that this information can be tracked as well. Patients will stop drug diary at time of stent removal.

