# **5.5 DATA ANALYSIS**

The main hypothesis of the non-inferiority of hyoscyamine to tamsulosin for treating lower urinary tract symptoms will be tested using a t-test for non-inferiority of the change in USI between POD1 and POD7 (or day of stent removal if removed before day 7) in each treatment arm. This should be slightly more powerful than the t-test at POD7 alone that we used to estimate the sample size, but there are not enough data available for the distribution at POD1 in order to make a good estimate of the change. The non-inferiority margin will be 15% of the change in USI. The primary analysis will be conducted as intention-to-treat (ITT). That is, subjects will be analyzed as belonging to the arm they were randomized to, irrespective of later crossover or other modifications. This approach is in line with the current statement on Consolidated Standards of Reporting Trials (CONSORT). Descriptive statistics will be used to describe the results from all USSQ domains at each timepoint (i.e. mean and standard deviation, along with confidence intervals for urinary symptom index, pain symptom index, etc.). We will also conduct non-inferiority tests of change in score for ITT with hyoscyamine versus tamsulosin for the other domains spanned by the USSQ, including pain symptom index, general health index, work performance index, and sexual matters between POD1 and POD7, although we may not be wellpowered to detect non-inferiority for these additional domains.

The secondary goal of determining if there are differences in the amount of additional medications need to treat stent-related discomfort between treatment arms will be examined primarily through descriptive statistics. The drug diaries of all subjects will be used to tabulate the kinds and amounts of additional medications used. For each subject, the number of days that additional medications were used will be counted. The proportion of days that additional medications were used will be calculated for each group and 95% confidence intervals will be calculated.

Finally, we will also calculate the informed consent rate, and the discontinuation rate for those patients needing to be removed from the study in each arm.

In all cases, a p-value  $\leq$  .05 will be taken as a statistically significant result.

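### The secondary objective asks whether additional medication use differs between arms, but section 5.5 estimates no between-arm difference and leaves the unit of analysis and CI method open

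*Combined protocol and SAP*

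**What the plan says.** The question is comparative wherever it is posed. Section 3.2 sets the objective: "To determine if there is a difference between the amount of additional medications needed to treat stent related discomfort", hyoscyamine versus tamsulosin. Section 1.1 adds a hypothesis that "patients in the hyoscyamine arm will not require additional pain medications" when set against the tamsulosin arm.

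Section 5.5 repeats the goal as one of differences between arms and says that it "will be examined primarily through descriptive statistics". Three outputs follow:

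- a tabulation: "The drug diaries of all subjects will be used to tabulate the kinds and amounts of additional medications used";
- a count per patient: "For each subject, the number of days that additional medications were used will be counted";
- a summary per arm: "The proportion of days that additional medications were used will be calculated for each group and 95% confidence intervals will be calculated".

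The section ends with a rule for all analyses that a p-value of .05 or less "will be taken as a statistically significant result". No test is named for this objective.

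On diary length, section 5.3 says "Patients will stop drug diary at time of stent removal". The footnote to the schedule in section 5.6 allows removal before or after day 7, and exclusion criterion 13 rules out stents planned for more than 2 weeks. The number of diary days therefore varies from patient to patient.

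**The concern.** Two per-arm intervals do not estimate a difference. A reader who wants the answer to objective 3.2 must form the comparison unaided, and the plan does not say how.

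The per-arm interval is also under-specified. The only per-patient quantity defined is a count of days. No per-patient denominator or proportion is given, and the proportion first appears at arm level. Dividing all days of use in an arm by all diary days in that arm, with a binomial interval, would fit the sentence. Days from one patient are likely to be alike, since a patient with a painful stent tends to need medication on several days. Such an interval would then claim more precision than the data hold.

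Pooling would also weight patients by diary length, without the plan saying that this is intended.

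At stake is the credibility of the rescue-medication result. Section 5.3 permits narcotics or Pyridium in either arm, so readers of the primary result will look to this comparison for context. The trial is open-label, which is a further reason to fix the method in advance.

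**Working it through.** **1. Is there a planned figure to reproduce?** None exists for this objective. The only design figure, about 47 per arm in section 5.4, belongs to the primary test. With CV .25, margin .15, one-sided alpha .025 and 80% power, n = 2(1.960 + 0.842)² × .25² / .15² = 43.6, so 44 per arm. The noncentral t gives 45, and power at 47 is 82.1%. That is close to the stated 47. Below, 47 serves only as the number of patients per arm.

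**2. Objective against analysis.**

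| Needed for objective 3.2 | Found in 5.5 |
|---|---|
| Estimate of the between-arm difference or ratio | None |
| Interval for that difference | None; an interval for each arm only |
| Test or model | None named |
| Unit of analysis for the proportion | Not stated |
| Method for the per-arm interval | Not stated |
| Handling of unequal diary length | Not stated |

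No other section fills these gaps.

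**3. What a pooled-day interval would do.** Inputs that are assumptions, not in the documents: m = 7 diary days per patient; intraclass correlation (ICC) of days within patient .1, .3 and .5; proportion of days p = .3 for the half-widths.

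- Patient-days per arm: 47 × 7 = 329.
- Design effect: DE = 1 + (m − 1) × ICC.
- Effective independent days: 329 / DE.
- Coverage of a nominal 95% interval: 2Φ(1.96/√DE) − 1.
- Half-width for the between-arm difference: 1.96 × √[2p(1 − p)/329 × DE].

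| ICC | DE | Effective days | Coverage of pooled-day CI | Half-width for difference, clustering allowed for |
|---|---|---|---|---|
| 0 | 1.0 | 329 | 95% | 7.0 points |
| .1 | 1.6 | 206 | 88% | 8.9 points |
| .3 | 2.8 | 118 | 76% | 11.7 points |
| .5 | 4.0 | 82 | 67% | 14.0 points |

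For example, at ICC .3: DE = 1 + 6 × .3 = 2.8, and 2Φ(1.96/1.673) − 1 = .759.

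**4. Simulation check.** Beta-binomial data were simulated with 47 patients per arm, 7 days each, p = .3 and .5, and 4,000 runs. Pooled-day coverage was 87–89%, 74–77% and 65–68% at the three ICCs, in line with the formula. An interval with the patient as the unit covered 94–95% throughout. If someone tested the arms on pooled days, which the plan does not propose, type I error would be 11–13%, 24–25% and 32–34%. With the patient as the unit it stayed at about 5%.

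**5. Weighting.** In a pooled proportion a 14-day diary counts 14/7 = 2 times as much as a 7-day diary. The documents give no distribution of stent times, so the size of this effect cannot be worked out.

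**The case against.** The strongest defence is that section 5.5 openly declares this analysis mainly descriptive. The objective is secondary and carries no power claim. The tabulation of kinds and amounts speaks directly to the amount of medication named in 3.2, so it is not true that a pair of intervals is all the plan offers. This stands as far as it goes, but describing each arm still does not determine whether they differ, which is what 3.2 asks.

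A reader might infer that the planned interval ignores clustering. The documents do not support that. The interval method is unstated, and the sentence just before it counts days for each subject, which fits an interval over patients equally well. The coverage losses apply only if days are pooled, and they rest on assumed correlations and diary lengths.

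A reader might also infer that the arms would be compared by whether the two intervals overlap. The plan states no such rule, so criticism of that rule is not criticism of this plan.

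Finally, weighting by days is not wrong in itself. The share of all stent-days with additional medication is a legitimate quantity, but the plan should say whether that quantity or the average patient's proportion is meant.

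**Conclusion.** The concern holds in two parts of different strength. The first is certain from the text: the objective is comparative, and no between-arm estimate, interval or test is planned. The second is conditional: because the unit and interval method are open, a compliant analyst could report an interval whose true coverage is about 88% to 67% instead of 95%, for assumed ICCs of .1 to .5 and 7 diary days per patient. If the interval is built over patients, that loss disappears.

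This is more than missing detail, since a specific and better analysis of data already being collected would answer the stated question. It should be corrected before the data are analysed. It concerns a secondary objective only, and the primary non-inferiority test does not depend on it.

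**What to change.** In section 5.5:

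- Name the patient as the unit of analysis. For each patient, compute the proportion of diary days with any additional medication, with diary days running from stent placement to stent removal, and say how a day with no diary entry is treated.
- Report the hyoscyamine minus tamsulosin difference in the means of these proportions, by randomized arm, with a 95% CI from a two-sample t-interval. A bootstrap over patients is an acceptable alternative; choose one in advance.
- Keep the per-arm proportions, with intervals over patients, and the tabulation by kind of medication as description. Do not add tablets across unlike products: Pyridium and the two narcotic preparations named in 5.3 are not interchangeable units.

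The cost is a few sentences and minor analysis work, with no new data. The interval will be wider than a pooled-day one. Under the assumptions above with p = .3, its half-width is about 9 to 14 points, against 7 if days were treated as independent. With about 47 patients per arm it may therefore leave the question open, and the report should say so if it does.

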# 5.4 STUDY DESIGN AND SAMPLE SIZE

Total sample size: 100

The study will be conducted as a randomized comparative effectiveness trial with two arms. Subjects will be randomized to one of two treatments WITH either hyoscyamine or tamsulosin. Our hypothesis is that the hyoscyamine is at least as effective as tamsulosin in treating lower urinary tract symptoms. Symptoms will be quantified using the Urinary Symptom Index (USI) of the validated Ureteral Stent Symptom Questionnaire (USSQ). To address the hypothesis, the study will be conducted as a non-inferiority trial, following the hypothesis that hyoscyamine is not inferior to tamsulosin by more than a 15% margin in terms of the USI. The sample size was estimated using the PowerTOST package for the R statistical environment, based on a nominal power of 80% and an alpha-level of .025 for the one-sided t-test. Our null hypothesis is therefore that the mean USI for those treated with tamsulosin is more than 15% greater than those treated with hyoscyamine, so that by rejecting it, we may conclude hyoscyamine is not-inferior to tamsulosin by more than a 15% margin of USI for treating lower urinary tract symptoms. Furthermore, we assume that the coefficient of variation (CV) for the mean Urinary Index Score

will be similar to that in Park, et al.20 The CV in that study for the Urinary Symptom Index at week 2 after stent placement for the tamsulosin group was approximately .25. This is slightly higher, but similar to the CV of .22 for the USI in Maldonado-Avila, et al. which collected data at week 1, and therefore should be slightly conservative.21 Using these assumptions, we estimated that the sample size for each arm would need to be approximately 47, in order to have the desired power.

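### Section 5.5 calls any p-value of .05 or less significant without stating sidedness, while Section 5.4 sizes the one-sided non-inferiority test at .025; read literally, the false non-inferiority rate at a fixed margin doubles

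*Combined protocol and SAP*

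**What the plan says.** Section 5.4 (Study Design and Sample Size) frames the trial as non-inferiority with a 15% margin on the Urinary Symptom Index (USI). Its sample size is "based on a nominal power of 80% and an alpha-level of .025 for the one-sided t-test", giving about 47 patients per arm.

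Section 5.5 (Data Analysis) says that the main hypothesis "will be tested using a t-test for non-inferiority of the change in USI between POD1 and POD7" (or the day of stent removal, if earlier), and it plans the same kind of test for the other USSQ domains. It gives no alpha, sidedness or confidence level for any of these tests. The only confidence level stated in 5.5 is 95%, and it belongs to the proportion of days on additional medication.

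The last sentence of 5.5 opens with "In all cases, a p-value", sets the threshold at .05 or less, and ends "05 will be taken as a statistically significant result". It does not say whether p is one-sided or two-sided, and it makes no exception for the non-inferiority tests.

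**The concern.** A non-inferiority t-test of the kind described in 5.4 yields a one-sided p-value. Comparing that p-value with .05, as the closing sentence of 5.5 literally directs, is a different decision rule from the one used to size the trial.

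Any one-sided p between .025 and .05 would then be a success under 5.5 and a failure under 5.4. The primary conclusion would depend on which section is followed, and the plan does not settle this before the data are seen. That matters more here because the trial is open-label.

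**Working it through.** **Inputs from the plan.** One-sided alpha .025, power 80%, margin 15% of mean USI, CV .25 (with .22 cited from a second study) and 47 per arm, all from 5.4; threshold .05 from 5.5.

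**Assumed, because the plan does not say.** Normal data, equal variances, higher USI is worse, a true difference of 0 for sizing, and the raw (not log) scale. All quantities are fractions of mean USI.

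**1. The plan's own sample size.** The normal approximation is n = 2(z₁₋α + z₀.₈₀)²(CV/margin)².
- One-sided .025: 2 × (1.960 + 0.842)² × (.25/.15)² ≈ 43.6, so 44 per arm. The noncentral t gives 45, within two patients of the stated 47.
- One-sided .05: 35 per arm, or 36 with the noncentral t.

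The stated 47 therefore fits the .025 design better. This is supportive only. The plan does not give the scale or the true ratio entered in PowerTOST, and other settings at .025 with no true difference give 38 to 67 per arm. Some equivalence (TOST) settings at .05 also fall near 47 (48 and 49).

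**2. Type I error at the margin.** For a fixed margin the rate equals the threshold applied to the one-sided p, whatever the CV or n. A simulation of 400,000 trials with the true difference at the margin gave:

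| Rule | False non-inferiority |
|---|---|
| one-sided p ≤ .025 | 2.50% |
| one-sided p ≤ .05 | 5.02% |
| two-sided p ≤ .05, favourable direction | 2.50% |

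**3. Where the two rules disagree (illustration).** SE = .25 × √(2/47) = .0516, with 92 degrees of freedom. Non-inferiority is concluded if the observed hyoscyamine disadvantage is below .15 − t × SE.
- At .025: .15 − 1.986 × .0516 = .0476
- At .05: .15 − 1.662 × .0516 = .0643

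An observed disadvantage between 4.8% and 6.4% of mean USI passes one rule and fails the other. At CV .22 the limits are 5.99% and 7.46%.

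**4. How often that happens (noncentral t, 47 per arm).**

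| CV | True disadvantage | P(non-inferior) at .025 | at .05 | Difference |
|---|---|---|---|---|
| .25 | 0 | .821 | .893 | .072 |
| .25 | .075 (half the margin) | .301 | .420 | .119 |
| .22 | 0 | .905 | .949 | .044 |

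Steps 3 and 4 describe the test used for sizing. The primary test is on the change from POD1 to POD7, and its power cannot be derived, because 5.5 itself says "there are not enough data available for the distribution at POD1".

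**The case against.** The strongest reply is that .05 is the conventional two-sided level. Read in the favourable direction it equals one-sided .025, so 5.4 and 5.5 agree and nothing is inflated. Section 5.4 ties .025 to the primary null hypothesis, and 5.5 refers back to the t-test used for sizing, so the specific statement could govern the general one. This reading is possible, and for that reason the inflation is stated as conditional. But no sentence says it. The test is described as one-sided, and the closing rule is worded to cover everything.

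The .05 rule might also have been meant for other tests. Section 5.5 handles additional medication primarily by description, which leaves some room for tests, and Section 3.2 has an objective on contributing factors with no method given. Even so, no such test is specified, and the non-inferiority tests are not excluded.

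Three narrower points stand as limits on the size:

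- The disagreement range and its 7% and 12% chances rest on USI at a single time point, not on the change score, so they only illustrate.
- Section 5.5 sets the margin at 15% of the change. If that margin is estimated from the observed tamsulosin change and treated as fixed, the error rates move. With equal variances and 47 per arm, the critical t is multiplied by √(2/(1 + .85²)) = 1.078 if a larger change is better, giving about 1.7% and 3.8%. It is multiplied by √(2/(1 + 1.15²)) = .928 if a larger change is worse, giving about 3.4% and 6.3%. The ratio between the two rules stays near two.
- The null in 5.4 is that the tamsulosin mean exceeds the hyoscyamine mean by more than 15%. This does not match a hyoscyamine disadvantage if higher USI is worse, so the direction of the difference needs to be written down too.

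**Conclusion.** The concern holds. The decision rule in 5.5, followed as written, is not the rule the trial was sized for. Applied to the one-sided p-value with a fixed margin, it allows 5.0% false non-inferiority in place of 2.5%. That doubling does not depend on the CV, the sample size or the PowerTOST settings. It disappears only under a two-sided, favourable-direction reading that the plan does not state. The practical effect on this trial's conclusion is modest under the sizing assumptions, and it cannot be quantified for the change-score test. Because a harmless reading exists, this should be fixed but does not undermine the design.

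**What to change.** Replace the last sentence of 5.5 with:

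> Non-inferiority is concluded only if the one-sided p-value is ≤ .025 (equivalently, if the margin-side limit of the two-sided 95% confidence interval for the between-arm difference, with the direction of the difference stated, excludes the margin); two-sided p ≤ .05 applies only to two-sided comparisons.

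This adopts the alpha already used in 5.4, so the sample size is unchanged. The sentence presupposes a clearly defined margin and does not supply one. The cost is one sentence, submitted as a protocol amendment and approved by the IRB before implementation, as Section 6.1 requires. It should be in place before the outcome data are analysed.

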# **5.6 SCHEDULE OF EVENTS**

Visits	Enrollment	Stent Placement	POD1	POD2	POD3	POD4	POD5	POD6	POD7 A	POD30
USSQ	Х		Х						Х	Х
Randomization	Х									
Complete Medication Diary		Х	Х	Х	Х	Х	Х	Х	Х	
REDCap Survey			Х						Х	Х
Stop Medication									Х	

Footnotes: A = If stent is removed prior to day seven then USSQ will occur on day of stent removal and diary will be stopped. If stent is removed after day seven then USSQ will occur on day seven but the diary will be stopped on day of stent removal.

